7.1 Quality Control

7.1.1 Study design

Before the implementation of the IDM study, the medical affairs system will organize expert

and carry out demonstration. During the monitoring, the protocol may be amended according

to the prescribed procedure.

7.1.2 Personnel qualifications

Project personnel will be suitably qualified for the tasks assigned to them, the relevant

professional background of epidemiology, statistics, pharmacy, clinical medicine are

requested. According to IDM study, design a training plan and train the correlate person for

quality control.

Page 26 of 35

Ferring Pharmaceuticals (Asia) Co., Ltd.

7.1.3 Reports and Archiving of Study Documentation

All raw materials need to be preserved. The data in study database comes from the original file and is consistent with original. CRO will conduct reconciliation periodically during the study. All observations and lab results should be completed timely, exactly, correctly, normatively. The data must not be changed at will. All documents will be kept for 10 years by specialist.

7.1.4 Statistical Analysis

Professional bio-statisticians are involved in each stage of the IDM study. The process and the expression of the results must be standardized. The missing, unused, or redundant data must be explained. A statistical report will be conducted and be in line with IDM report.

7.2 Audit from Quality Assurance Unit

The Quality Assurance (QA) unit may audit the study to ensure that study procedures comply with the protocol and standard operating procedures, and that collected data is correct and complete.

7.3 Data Management

The patients' data will be input into the charity's database by the delegated staff. The patients will be identified only by Study ID and patient number in the export database for analysis.

If the written informed consent of a patient is known not to be available in spite of it being required, data for this patient is not entered into or is deleted from the export database.

If a patient is included in the study in spite of being treated off-label (not according to the summary of product pharmacological study), data is kept in the database and analysed separately and as part of the overall analyses as described in the Statistical Analysis Plan.

The safety data (AEs report) filed in AE form will be input into global safety database. The current Standard Coding Instructions for coding of medical history, concomitant illness (MedDRA), concomitant medication (WHO-Drug) and adverse events/reactions (MedDRA) must be followed.

Ferring Pharmaceuticals (Asia) Co., Ltd.

8 Statistical Methods and Determination of Sample Size

8.1 General Aspects

All analyses will be performed using SAS version 9.3 or above by the Biostatistician.

Numerical data are presented as number of patients, mean, standard deviation, median, min

and max. Categorical data are presented as frequency and percentage of patients. Missing data

will be analyzed as is, no imputation method will be utilized. The statistical analysis plan will

be finalized at least 1 week before the database lock.

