This study is a multi-center, single-arm, non-interventional, prospective study among Chinese patients with prostate cancer and need androgen deprivation therapy receiving treatment with FIRMAGON®. This program will provide the minimum 6 doses and maximum 12 doses of FIRMAGON® to enrolled patients during one-year follow-up. Patients who meet inclusion criteria and will or are accepting at least 6 self-financed doses treatment in hospital. Patients should return to the hospital for medical assessment every three months. The prescription of 6 (3 dose × 2 times) self-financed doses will be given by doctors after assessment, and the direct-to-patient pharmacy will distribute FIRMAGON® to eligible patients (patients should bring the prescriptions and the last FIRMAGON® boxes to get other doses). All enrolled patients will be followed up to collect safety information for one year from the 1st dose unless withdrawal of Informed Consent Form, discontinuation for 2 months, lost to follow-up, death, or termination due to other reasons, whichever comes first.

• Study sites

Data will be collected by China Primary Healthcare Foundation from patients or Health care providers (HCPs). 138 target hospitals are in the charity support list.

Patients number

2500 patients who are prescribed FIRMAGON® according to clinical practice by doctors in hospitals will be enrolled in this study.

• Main Inclusion Criterion

Patients must meet all the criteria listed below to be eligible for participation in the project.

- > Diagnosis with prostate cancer and need androgen deprivation therapy
- > Decision made to prescribe of FIRMAGON® prior to enrolment.
- Willingness and ability to provide written informed consent.
- The patients are from whom taken post-marketing drug FIRMAGON®.

• Main Exclusion Criterion

Any patient who meets the following criterion will not be qualified for the entry of this study:

- Not sign Informed Consent.
- Any patients who is unsuitable to participate in this study because of any other reasons will not be qualified to participate in this study.
- Data collection

The data below will be collected based on the current clinical practice and no additional data, diagnostic or monitoring procedures are applied to the patients.

Patient demographic information of age

Intensive Drug Monitoring Protocol Version: 1.0

Date: 11-May-2020

- Disease characteristics: PSA and Testosterone

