1.3 Preliminary safety assessment results

Domestic Clinical Trials

The safety of Degarelix was investigated in a China Phase III active-controlled trial in Chinese patients (N = 283) receiving monthly Degarelix (subcutaneous injection) or Goserelin (subcutaneous injection) for 12 months. Adverse events reported in $\geq 5\%$ patients were showed in Table 1.

Table 1, Adverse Events occurred in >=5% Patients in the Groups by MedDRA System Organ Class and Preferred Term - Safety Analysis Set

	Degarelix 240/80mg	Goserelin 3.6mg
	(S.C.)	(S.C.)
	N=142	N=141
Any Adverse Event	76.1%	58.9%
General Disorder and administration site condition		
Injection site reactions	45.1%	1.4%
Injection Site Swelling	26.8%	0.7%
Injection Site Erythema	26.8%	
Injection Site Pain	24.6%	0.7%
Injection Site Mass	7.0%	
Pyrexia	12.7%	1.4%
Fatigue	5.6%	2.1%
Infections and Infestations		
Urinary tract infection	7.0%	7.8%
Vascular Disorders		
Hypertension	9.9%	10.6%

MedDRA version 18.0

Ferring Pharmaceuticals (Asia) Co., Ltd.

The most common adverse events in patients treated with Degarelix were injection site reactions, including injection swelling (26.8%), injection site erythema (26.8%), injection site pain (24.6%), and injection site mass (7.0%).

Most injection site reactions were mild or moderate in severity (2 patients with severe injection site reactions: 1 with severe injection erythema and 1 with severe injection site mass), and there is no hypersensitivity reaction of immediate onset. Adverse events mainly occurred in the initial stage of treatment, and their incidences were decreased with time. No patients discontinued from the trial due to injection site reactions.

Of abnormalities in hepatic function test, alanine aminotransferase (ALT) (with or without total bilirubin), aspartate aminotransferase (AST), and total bilirubin were comparable between the treatment groups. No patient developed increased ALT considered as serious adverse event, and no patient discontinued from the trial due to increased ALT.

ECG results showed that, there was no significant differences of mean change of QTcF between the treatment groups from baseline to Day 3 and to the end-of-trial visit.

QTcF >=500 msec occurred in 13 patients, including 7 (5%) patients in the Degarelix Group and 6 (4%) patients in the Goserelin Group.

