Overall, the safety results from the trial were consistent with those of foreign pivotal studies, and were also consistent with the expected results in elderly patients of prostate cancer receiving androgen therapy; mo major safety problems were found.

Available data from clinical trials indicates that FIRMAGON® is generally well tolerated, with adverse events (AEs) generally being manageable and reversible with supportive care. The adverse event profile is similar to that of the GnRH agonists with the most frequently reported adverse drug reactions (ADRs) being related to the pharmacological activity of the product (testosterone inhibition). See detail information from China label of Degarelix .

Regulatory requirements

The China National Medical Products Administration (NMPA) on 11 Sep, 2018 formally approved the Marketing Authorization Application of imported FIRMAGON® in China. Due

Intensive Drug Monitoring Protocol Version: 1.0

Date: 11-May-2020

to the requirements on "Regulations for the Reporting and Monitoring of Adverse Drug Reactions" and the "Intensive Drug Monitoring Guidelines for Manufacturers", Marketing Authorization Holder (MAH) should report all adverse reactions and conduct intensive monitoring for new imported drugs within 5 years from the date of first approval.

Intensive Drug Monitoring (IDM) refers to drug safety monitoring activities carried out to further understand clinical use of drug, the occurrence of ADRs and its occurrence of characteristics or seriousness or incidence in real world practice. Based on the consideration, Ferring Pharmaceuticals (Asia) Co.,Ltd. (hereinafter referred to as "Ferring") plans to carry out IDM study and collect all patients' AEs whether or not related to the product use, with particular attention to the occurrence of important adverse reactions.

Ferring Pharmaceuticals (Asia) Co., Ltd.

2 Study Objective and Outcome measure

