This study is a multi-center, single-arm, non-interventional study among Chinese patients with prostate cancer needed androgen deprivation therapy receiving treatment with FIRMAGON®. 2500 patients who are prescribed FIRMAGON® according to clinical practice by doctors in hospitals will be enrolled in this study. This program will provide the minimum 6 doses and maximum 12 doses of FIRMAGON® to enrolled patients during one-year follow-up. Patients apply for enrollment in hospital, they will return to hospital every three months for medical assessment and other three doses of FIRMAGON® prescription during the study. 138 target hospitals are in the charity support list. The direct-to-patient pharmacy will distribute FIRMAGON to patients who are defined eligible by the doctor. The patient should bring the prescriptions and the last FIRMAGON® boxes to get other FIRMAGON®.

All enrollment patients will be followed up to collect safety information for one year from China Primary Healthcare Foundation from the 1st dose unless withdrawal of Informed Consent Form, dosing interrupted for 2 months or more than 2 months since last dose, lost to follow-up, death, or termination due to other reasons (defined in section 5.4), whichever comes first. Any AEs will be filled in Adverse Event Form (as Appendices), processing and submitting to relevant authorities.

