5.3 Selection of Study Population

5.3.1 Inclusion Criteria

Patient eligibility is determined according to the following criteria prior to entry into the

study:

1) Diagnosis as prostate cancer and need androgen deprivation therapy

2) Decision made to prescribe of FIRMAGON® prior to enrolment.

3) Willingness and ability to provide written informed consent.

4) The patients are from whom taken post-marketing drug FIRMAGON®.

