6.3 Collection and Recording of Adverse Events

The safety data will be actively collected in accordance with the follow-up time in the study plan. Patients and HCPs could report AE spontaneously after follow-up time. Collection and recording of SAEs and AEs will commence once the study participant has started first dose of

FIRMAGON®.

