8.3 Statistical Methods

Descriptive statistics will be performed of all collected data except data collected only for the

purpose of data cleaning. No formal hypothesis will be tested in this study. If necessary,

Fisher's exact test, $\chi 2$ test will be used to examine differences in AEs occurrence between

subgroups (It will be defined based on the enrollment patients).

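### Cheap improvement: section 8 reports adverse events only as crude counts and percentages, with no confidence interval and no measure that allows for follow-up ending before one year

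*Combined protocol and SAP*

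**What the plan says.** - **Summary measure.** Section 8.1: "Categorical data are presented as frequency and percentage of patients". Missing data are analysed as they stand, without imputation. Section 8.2 puts every analysis on the full analysis set (FAS), which requires consent and treatment but no minimum follow-up.
- **Methods.** Section 8.3: "Descriptive statistics will be performed of all collected data", apart from data-cleaning items. There is no formal hypothesis. Fisher's exact or chi-square tests between subgroups are allowed if needed, on the same proportions.
- **Follow-up.** Section 5 plans one year from first dose, ending sooner on consent withdrawal, "dosing interrupted for 2 months or more than 2 months since last dose, lost to follow-up, death, or termination due to other reasons". Section 5.4 lists further reasons.
- **Purpose.** The regulatory paragraph at the end of section 1 says intensive monitoring is meant to describe "the occurrence of ADRs and its occurrence of characteristics or seriousness or incidence in real world practice".
- **Timing of AEs in the earlier Chinese trial.** Section 1.3: "Adverse events mainly occurred in the initial stage of treatment, and their incidences were decreased with time".
- **Entry and start of AE recording.** The study summary describes patients who "will or are accepting at least 6 self-financed doses treatment in hospital", so some may already be on treatment. Section 6.3: "Collection and recording of SAEs and AEs will commence once the study participant has started first dose of" the drug. Section 6.1.1 likewise asks for all AEs after the first dose, and the section 5.6 table ticks AE collection at baseline.
- **Dates.** Section 5.6 lists AE onset and stop dates, time of initial dose and treatment duration. Neither 5.4 nor 5.6 names an end-of-observation date.

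**The concern.** AE data are the main purpose of the study (section 5.2). In a crude percentage, a patient who leaves event-free at month 2 weighs the same in the denominator as one observed for twelve months. For an event that accrues with exposure, a low percentage can therefore mean low risk or short observation, and n and N alone cannot separate the two. The optional subgroup tests inherit the problem: subgroups with different retention could appear to differ in AE risk.

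The missing intervals matter less. A reader can compute them from n and N, but printing them shows at once how little a rare or unseen event rules out.

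**Working it through.** The plan has no figure of its own to reproduce here. The 2500 comes from a regulatory guideline and discussion with the authority (section 8.5), with no precision target or exit rate.

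**Inputs.** N = 2500 and one-year follow-up are from the protocol. Assumed: true 12-month risk 10%; share leaving by month 12 d = 10, 20, 30 or 40%; exit unrelated to the event and not by death.

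**Formula.** With time in years, H = −ln(0.9) = 0.1054 and M = −ln(1 − d), the expected crude proportion is the integral over 0 to 1 of h(t) × exp(−H(t)) × S_exit(t), where h(t) is the event hazard, H(t) its cumulative value and S_exit(t) the proportion not yet gone.

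*Constant hazard, exit from day 0:* H/(H+M) × [1 − exp(−(H+M))]. At d = 30%, M = 0.3567: 0.1054/0.4620 × (1 − 0.6300) = 0.2280 × 0.3700 = 8.44%.

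*Constant hazard, exit only in months 6–12:* 1 − exp(−H/2) + exp(−H/2) × H/(H+2M) × [1 − exp(−(H+2M)/2)]. At d = 30%: 0.0513 + 0.9487 × 0.1287 × 0.3359 = 9.23%.

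*All risk in month 1, exit from day 0:* 12H/(12H+M) × [1 − exp(−(H+M/12))]. At d = 30%: 0.7800 × 0.1264 = 9.86%.

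Expected crude percentage when the true 12-month risk is 10%:

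| Event timing | Exit | d = 10% | 20% | 30% | 40% |
|---|---|---|---|---|---|
| Constant hazard | from day 0 | 9.50 | 8.98 | 8.44 | 7.87 |
| Constant hazard | months 6–12 only | 9.75 | 9.50 | 9.23 | 8.95 |
| Half the hazard in month 1 | from day 0 | 9.71 | 9.41 | 9.09 | 8.76 |
| Half the hazard in month 1 | months 6–12 only | 9.87 | 9.73 | 9.58 | 9.43 |
| All in month 1 | from day 0 | 9.96 | 9.91 | 9.86 | 9.79 |
| All in month 1 | months 6–12 only | 10.0 | 10.0 | 10.0 | 10.0 |

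**Against sampling error** (exact Clopper-Pearson 95% limits). Constant hazard with late exit: 231/2500 (d = 30%) gives 8.13–10.44% and 224/2500 (d = 40%) gives 7.87–10.15%; both cover 10%, as does every late-exit case. Only the heavier day-0 cases miss it: 211/2500 gives 7.38–9.60% and 197/2500 gives 6.85–9.01% (constant hazard, d = 30% and 40%); 219/2500 gives 7.68–9.94% (half in month 1, d = 40%).

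**Rare events.** For 0/2500 the upper limit is 1 − 0.025^(1/2500) = 0.147%. For 5/2500 (0.2%) the limits are 0.065–0.466%.

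**Patients already on treatment at enrolment.** Simulated with 30% annual exit after enrolment and half the patients entering evenly over months 0–6 after first dose. With AEs recorded back to the first dose, as 6.1.1 and 6.3 ask, ordinary time-to-event estimation from first dose returns 10.0% for the constant and the half-in-month-1 hazard. If AEs before enrolment are not recorded and time is still counted from first dose, it returns about 8.7% and 7.2%; delayed entry restores 10.0%.

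**The case against.** **The SAP is still to come.** Section 8.1 has it finalised at least one week before database lock, and intervals and rates are normal SAP content. This stands in part: the plan may yet include them. But nothing in section 8 calls for them, and a late SAP cannot recover a date that was never recorded.

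**The protocol does not name 12-month risk as its measure.** Correct. Section 2.1 speaks of the occurrence of AEs, and incidence appears only in a general description of intensive monitoring. The crude percentage is therefore not wrong. A reader might infer that the planned AE results are invalid; the documents do not support that.

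**The bias may be small.** Also fair. No exit rate is given, the programme is built around at least six doses (which makes late exit plausible without guaranteeing it), and AEs in the earlier trial came mainly early. In those settings the loss lies within sampling error.

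**Patients already on treatment.** A reader might infer that the plan loses their AEs before enrolment and so biases any time-based estimate to 8.7% or 7.2%. The text says otherwise: sections 6.1.1 and 6.3 start collection at the first dose. Those figures arise only if sites do not record the earlier events. The inclusion criterion "The patients are from whom taken post-marketing drug" is too unclear to settle who is already treated.

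**The missing date.** A reader might infer that no end-of-follow-up date will exist. Section 5.4 requires discontinuation events to be recorded, 5.6 asks for details of permanent withdrawals, and the database specification is not in the file. What can be said is that the date is not named, and that loss to follow-up is not in the 5.4 list.

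**Conclusion.** The point holds as a cheap improvement. No section names an interval or a time-adjusted measure, while the design lets follow-up end early.

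For AEs that accrue evenly, the crude percentage understates a 10% 12-month risk by about 5–21% in relative terms if exit runs from day 0, and by about 2.5–10.5% if exit is confined to months 6–12. For events all in month 1 the loss is at most about 2%. These sizes rest on assumed exit of 10–40%, non-informative exit and the stated hazard shapes. Exit by death is a competing event and not a loss of this kind. The intervals alone are a reporting gain.

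**What to change.** In section 8.3 or the SAP:

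1. Keep crude n (%) and add exact 95% confidence intervals, including the upper limit for zero-event terms of interest.
2. For any AE, SAE, ADR and the main preferred terms, add 12-month cumulative incidence from first dose (Aalen-Johansen, death competing) with a 95% confidence interval.
3. Summarise follow-up time and the reasons for ending it.
4. Before enrolment, confirm that one end-of-observation (last-contact) date is recorded per patient, including those lost to follow-up; add the field if it is absent.
5. For patients already on treatment at enrolment, record AEs back to the first dose as 6.1.1 and 6.3 ask. Use delayed entry only as a sensitivity analysis, or if those AEs cannot be recorded reliably. Show patients who start treatment at enrolment separately.
6. State that exit because of an AE makes censoring informative, so some bias can remain.

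Cost: SAP wording, a few extra tables and possibly one date field. AE onset date, time of initial dose and treatment duration are already collected. Treatment, eligibility and sample size do not change.

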8.2 Analysis set

The full analysis set (FAS) will include inpatient or outpatient prostate cancer patients signed

informed consent and who need androgen deprivation therapy and have received

FIRMAGON® treatment. All analyses will be performed on the FAS population.

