5.4 Patient Discontinuation

The following events will result in patient discontinuation and should be recorded in the study database:

- 1) The doctors confirm that the patient does not meet the instructions of FIRMAGON® or is unsuitable for continued use;
- 2) The patient presents an intolerable adverse reaction;
- 3) Death;
- 4) The patient, his legal guardian or immediate family request the discontinuation of FIRMAGON® treatment;
- 5) The patient refuses to accept medical evaluation according to the procedure or protocol;
- 6) The patient automatically removes from the group after 2 months discontinuation of medication;
- 7) The patient sales, exchanges the donation drugs for profit purposes;
- 8) The application information provided by patients is confirmed as false information, including application form with patient's information, medical information (medical history, diagnoses, treatment, etc.) and follow up information, etc;;
- 9) The application is not within the time limit, or all the donation drugs have been distributed within cutoff day;
- 10) Suspension due to the policy adjustments or changes from regulatory authority.

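### Section 8.2 leaves consented, treated patients without the indication out of every analysis, while 7.3 keeps off-label patients in

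*Combined protocol and SAP*

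**What the plan says.** Section 8.2 (Analysis set) gives the only population definition. It opens with the disease: "The full analysis set (FAS) will include inpatient or outpatient prostate cancer patients signed". The rest of that sentence sets out consent, need for treatment and exposure: "informed consent and who need androgen deprivation therapy and have received" the study drug. It adds: "All analyses will be performed on the FAS population". No separate all-treated safety set is defined.

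Section 7.3 (Data Management) has two rules that bear on who is analysed:

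- Where required written consent is known to be missing, "data for this patient is not entered into or is deleted from the export database".
- For off-label use, the condition is "If a patient is included in the study in spite of being treated off-label". The handling is then that "data is kept in the database and analysed separately and as part of the overall analyses as described in the Statistical Analysis Plan".

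Section 5.4 (Patient Discontinuation) lists reasons for stopping that are to be recorded in the study database. Item 1 includes "The doctors confirm that the patient does not meet the instructions of FIRMAGON". Item 8 covers application information confirmed to be false, with diagnosis among the examples.

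Section 8.3 promises descriptive statistics on all collected data, apart from data held only for cleaning. Section 6.1.1 asks for all adverse events (AEs) after the first dose. Section 8.1 requires the SAP to be final at least one week before database lock.

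**The concern.** In a safety study, exposure should decide who is in the denominator. Section 8.2 adds a condition on disease and treatment need, and no other set picks up the treated patients who do not meet it. Their AEs would be collected under 6.1.1 but would appear in no table of the study report. Section 7.3 promises that off-label patients count in the overall results and are also shown separately.

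Two rules that give different denominators leave the choice to whoever writes the tables. The SAP may be settled as late as one week before lock. In a single-arm study most AEs will be known by then, so a rule based on exposure is safer if fixed in the protocol.

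**Working it through.** The plan gives no figure to reproduce. Its 2,500 patients come from a regulatory requirement lowered after discussion with the authority (8.5), not from a formula. The check is to take each type of treated patient through both sections.

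| Treated patient | Under 8.2 | Under 7.3 | Conflict? |
|---|---|---|---|
| (a) Consented, but no prostate cancer or no need for ADT (fails inclusion 1) | Outside the FAS, so in no analysis | If off-label: kept, shown separately and overall | Yes |
| (b) Consented, has prostate cancer and needs ADT, off-label in some other way | In the FAS | Kept, shown separately and overall | No |
| (c) Consented, has prostate cancer and needs ADT, but fails inclusion 2 or exclusion 2 | In the FAS | Not addressed | No |
| (d) Required consent known to be missing | Outside the FAS | Not entered, or deleted | No |

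Only type (a) conflicts. The conflict needs one premise that the documents do not supply: that treating such a patient is off-label.

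**Can type (a) occur?** Inclusion 1 (5.3.1) is checked before entry, and the 5.6 table has an inclusion/exclusion row at baseline, so few should be enrolled. Items 1 and 8 of 5.4 are reasons for discontinuation, however, so the plan accepts that such facts may emerge later, including after dosing. Section 8.2 does not say whether the baseline check or a later finding decides FAS membership.

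**How large could the effect be?** The documents give no number. Purely as an assumption, let a share f of 1% to 5% of the 2,500 be type (a):

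- Patients outside every table: 0.01 × 2,500 = 25, to 0.05 × 2,500 = 125.
- If these patients have the same AE risk as the rest, numerator and denominator both shrink by the factor (1 − f), and the expected rate is unchanged.
- For a rare event with 3 cases (3/2,500 = 0.12%), the expected number of cases lost is 3f, or 0.03 to 0.15. The chance of losing at least one is 1 − (1 − f)³, which is 1 − 0.99³ = 3.0%, to 1 − 0.95³ = 14.3%.
- If one case were lost, the rate would become 2/2,475 = 0.081%, to 2/2,375 = 0.084%, a fall of about 33% to 30%.

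On this assumption common AE rates would hardly move, and a visible change in a rare one is possible but unlikely.

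**The case against.** The strongest reply is that 8.2 merely describes the enrolled population. Eligibility is settled at baseline, nothing in 8.2 provides for reclassification after dosing, and 5.4 stops treatment without removing data. Section 7.3 already commits to counting off-label patients and leaves the detail to the SAP. Their AEs would in any case enter the global safety database and be handled as individual reports.

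Part of this stands. The baseline check is real, and item 1 of 5.4 need not mean that prostate cancer is absent. But 8.2 is written as a condition of membership, and read literally it excludes type (a). The SAP rule that 7.3 points to is not in the documents, so it cannot be shown to resolve the clash. Individual case reporting does not put a patient into the study's rates.

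A reader might infer more than the text supports:

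- **That every treated patient who fails eligibility is dropped.** Section 8.2 repeats only the diagnosis and ADT criterion, consent and exposure. Type (c) stays in.
- **That 7.3 keeps all ineligible patients.** It speaks of off-label treatment, and it removes patients without required consent.
- **That need for ADT is never recorded, so membership must be judged afterwards with AEs known.** The baseline inclusion/exclusion row in 5.6 covers it. What remains is that 8.2 does not say whether a later finding overrides that check.
- **That rare-event rates would be cut by a third.** This is the result if one of three cases happens to fall among the excluded. It is not the expected result, and no share of affected patients is stated.

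**Conclusion.** The point holds in a narrow form. Under 8.2 a consented, treated patient found not to have prostate cancer, or not to need ADT, is outside the only analysis set. Under 7.3 the same patient, if off-label, belongs in both a separate and the overall analysis. Both instructions cannot be followed, and 8.2 also sits badly with the promise in 8.3 to describe all collected data.

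The conclusion assumes that the approved indication matches the disease and treatment condition in 8.2. The number affected is unknown and probably small; the 1% to 5% range is illustrative. The point is still worth correcting, because the plan's primary purpose is safety and the present wording excludes exposed patients from every table.

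**What to change.** In 8.2, define the analysis set for safety as every consented patient who received at least one FIRMAGON injection, whatever is later found about indication. Flag off-label patients and tabulate them separately, as 7.3 already requires, while keeping them in the overall tables. Carry the same rule into the SAP so that 7.3, 8.2 and the SAP agree. The consent rule in 7.3 is unaffected.

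The cost is a reworded sentence in 8.2, a matching one in the SAP, and one extra table. No new data are needed and patient care does not change.
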